#### Matched Cohort Study

Using the whole CCP-UK prospective observational cohort, we will perform a matched cohort study. We will match cancer patients and non-cancer patients within the main dataset by age, sex, race and comorbidities. We will determine which factors are associated with fatal outcomes for patients with cancer, particularly with respect to cancer type, stage, immune suppressive or immune modulating/immunotherapy treatment, treatment intent and time from diagnosis.

Data from the CCP-CANCER UK CRF will be supplemented by linked data. Where a data field is discussed that does not appear in the linked data specification, it will be present in the electronic CRF.

We will examine the effects of the following variables on mortality and severity of COVID-19 in cancer patients:

- Age, Sex, Co- morbidities
- Tumour type
- Solid versus haematological malignancy
- Bone marrow transplant
- Stage of malignancy at time of COVID-19 (from CCP-UK CRF) and stage at diagnosis from data linkage.
- \*Diagnosis of malignancy in the last: 1-4 weeks, 1-6 months, 6 months -1 year, 1-5 years, > 5 years
- \*Surgery or Chemotherapy or radiotherapy treatment in the last: 1-4 weeks, 1-6 months, 6 months -1 year,
- > 1 year
- ¥Other systemic anticancer therapy in the last: 1-4 weeks, 1-6 months, 6 months -1 year, > 1 year
- Intent of treatment: Curative vs (neo)adjuvant vs palliative vs watch and wait
- Use of corticosteroids
- Use of Granulocyte colony-stimulating factor

#### \*From COVID-19 episode

¥ Endocrine therapy, Immunotherapy, Small molecules, Monoclonal antibodies

### 8.3. Study Endpoints

### 8.3.1. Primary Endpoint

The primary endpoint is patient fatality measured as a binary endpoint.

### 8.3.2. Secondary Endpoint

Secondary endpoints include:

- Time to death measured as the time from COVID diagnosis to death by any cause.
- Time to recovery measured as the time from diagnosis to recovery.
- ITU admission measured as a binary endpoint.
- Describing the clinical features and degree of severity\* of infection.
- Describing clinical and laboratory variables that correlate with COVID-19 severity and fatality rate.
- Describing the healthcare resource use.

\*Currently, severity of infection is defined as: Mild – no oxygen requirement, admission length < 7 days Moderate – ward level oxygen administered Severe – ITU admission, death, NIV, high flow oxygen administered

Severity definitions will be subject to change to keep them aligned with definitions used by the ISARIC4C consortium.

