#### 5.3. Co-enrolment Guidelines

All patients MUST be recruited in the Principal CCP-UK protocol. There are no further restrictions in relation this data collection with regard to recruitment into any clinical trials or research studies.

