# 6. Participant Identification, Assessments and Data Collection

### 6.1. Participant Identification and Screening

Where possible, a cancer co-investigator will be identified at each site prior to starting data collection for CCP-CANCER UK. They will be responsible for identifying a team to:

[figure not shown]
- Facilitate the completion of the CCP-CANCER UK REDCap Database (see section 9.3).
- Establish mechanisms to proactively identify patient admissions with SARS-CoV-2 infection and a current cancer diagnosis to allow prospective co-enrolment.

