#### **IDENTIFICATION of patients locally:**

Sites may also establish local mechanisms to identify patients who have been admitted with SARS-CoV-2 infection with a current cancer diagnosis. Any patients identified locally need to be enrolled in the Principal CCP-UK Study and then the cancer data set should be completed.

It is recognised that local arrangements for both ISARIC CCP-UK and CCP-CANCER UK will vary. Where the principal CCP-UK study is open at a different centre to the CCP-CANCER UK study cross centre collaboration should be used to get both datasets completed. If the inclusion criteria of enrolment into any Tier of the Principal CCP-UK protocol cannot be met the patient should not be included on the CCP-CANCER-UK study

No screening data will be collected as part of the study.

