## 6.4.4 Data linkage to determine population level risks in UK cancer patients

In addition to taking data from the ISARIC CCP-UK study, which provides a focussed look at in-hospital treatment of patients with COVID-19, to be able to generalise our findings to a national population, we will need to establish how many cancer patients develop COVID-19 and their subsequent treatments and outcomes. To do this, we will use linked data that are not restricted to the ISARIC CCP-UK study and instead take all individuals with cancer registration data available and link these to SARS-CoV-2 testing data, primary care data, secondary care data and national statistics registrations.

Data will be requested according to the same specification provided to cancer registry linkage providers and will request additional data points held in testing data, primary care data, secondary care data and national statistics registrations. Data flow will be from the providers directly into the Scottish National Safe Haven, as no patient identifier lists will be required.

These data will allow us to determine which populations are at the highest risk of COVID-19, both in hospital and in the community and establish a baseline rate in these settings. This will allow us to establish whether there are

particular patient groups who are more likely to be admitted to hospital or who will go on to die while in hospital, compared to patients who do not die or who remain in the community with positive tests. We request data for all patients, both for those with negative and positive SARS-CoV-2 tests or diagnoses. These data will also enable us to determine whether changes in practice have led to improved or worsened cancer outcomes over the time of the SARS-CoV-2 pandemic.

The data will not contain any identifiers and will not be able to be linked with the ISARIC CCP-UK or CCP-CANCER UK datasets.

For data linkage, we will capture variables including lower super output area. This will be used to map individual region rates of SARS-CoV-2 and determine other geographical variables including deprivation, distance to healthcare facilities and other socioeconomic deprivation markers linked with geography. We will not capture information on hospital of treatment in the linkage requests, as this will provide too logistically challenging to match back to hospital for recruitment purposes.

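### Time to death and time to recovery start at COVID-19 diagnosis, but the cohort is found through hospital admission, so any days from diagnosis to admission are survival by selection

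*Protocol*

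**What the plan says.** Section 8.3.2 lists two time-to-event secondary endpoints with the same origin: "Time to death measured as the time from COVID diagnosis to death by any cause" and "Time to recovery measured as the time from diagnosis to recovery". The date of diagnosis is not defined.

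Entry to the cohort depends on the parent study. Section 5.3 states "All patients MUST be recruited in the Principal CCP-UK protocol", and section 6.1 says that where this condition "cannot be met the patient should not be included on the CCP-CANCER-UK study".

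Several places describe that parent cohort as admitted patients:
- Section 6.4.4 says of CCP-UK that it is a study "which provides a focussed look at in-hospital treatment of patients with COVID-19".
- Section 6.1 asks sites to "Establish mechanisms to proactively identify patient admissions with SARS-CoV-2 infection and a current cancer diagnosis to allow prospective co-enrolment", and adds "Sites may also establish local mechanisms to identify patients who have been admitted with SARS-CoV-2 infection with a current cancer diagnosis".
- In section 8.3.2 even the mildest severity grade is defined partly by "admission length < 7 days".

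Section 5.1 itself asks only for enrolment in CCP-UK at any tier. Section 6.4.3 lists SARS-CoV-2 testing data among the linkages for England, Scotland and Wales. The protocol does not mention delayed entry, a landmark, or admission as a time origin.

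**The concern.** The clock starts at an event that can come before the point at which a patient can be observed. Someone who tests positive in the community and dies before reaching hospital is not in the cohort. For a member diagnosed some days before admission, those days are therefore free of death by construction, but the endpoint counts them as follow-up at risk.

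There are two consequences. Early mortality measured from diagnosis is too low and the median time to death too long. And if groups differ in how long before admission they are diagnosed, their curves and medians differ even when the course in hospital is the same. The note to section 3.3 asks for every objective to be compared with non-cancer patients and with other comorbid groups, so lag differences between groups matter. Time to recovery is stretched by the same interval.

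**Working it through.** The protocol states no figure for this endpoint that could be reproduced. The check sets the origin against the entry route, then shows the size under stated assumptions.

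**Origin against entry**
- Diagnosed before admission: the clock starts at diagnosis, the patient becomes observable at admission, and the interval is survival by selection.
- Diagnosed at or after admission: there is no such interval.

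**Inputs for the illustration**
- Fatality 10% (protocol section 8.2).
- Assumed: time from admission to death, among those who die, is gamma with shape 2 and mean 8 days, the same in both groups.
- Assumed: lag L from diagnosis to admission is Poisson. The protocol gives no lag.

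**Formula**

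Mortality by day t from admission is 0.10 × F(t), with F(u) = 1 − (1 + u/4)e^(−u/4).
- Day 7: F = 1 − 2.75 × 0.1738 = 0.522, so 5.2%.
- Day 14: F = 1 − 4.5 × 0.0302 = 0.864, so 8.6%.

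Mortality by day t from diagnosis is 0.10 × Σ P(L = k) × F(t − k), with F = 0 for negative arguments.

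| Mean lag (days) | Day 7 | Day 14 | Day 28 | Median time to death among deaths (days) |
|---|---|---|---|---|
| 0 (clock from admission) | 5.2% | 8.6% | 9.9% | 6.7 |
| 2 | 3.5% | 7.9% | 9.9% | 8.8 |
| 4 | 2.0% | 7.0% | 9.8% | 10.9 |
| 7 | 0.6% | 5.0% | 9.6% | 14.0 |

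The true difference between groups is zero in every row. With lags of 2 against 7 days, day-14 mortality is 7.9% against 5.0% and the medians are 8.8 against 14.0 days. By day 28 the curves nearly meet.

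**If only some patients are diagnosed early**

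Suppose 20% of one group and 40% of the other have a mean lag of 5 days (day-14 mortality 6.4% for those patients) and the rest have none.
- 0.20 × 6.4% + 0.80 × 8.6% = 8.2%.
- 0.40 × 6.4% + 0.60 × 8.6% = 7.7%.

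The gap falls to about half a percentage point.

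**Hazard ratios, longer-lag group against shorter-lag group**

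These come from simulation with follow-up to day 28. The true value is 1 on the clock that drives the hazard.

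| Assumed course | Lags (days) | Diagnosis clock as written | Diagnosis clock, delayed entry | Clock from admission |
|---|---|---|---|---|
| Gamma from admission, as above | 2 v 7 | about 0.93 to 0.96 | about 1.3 to 1.4 | about 1.0 |
| Gamma from admission, as above | 4 v 7 | about 0.97 to 0.98 | about 1.2 | about 1.0 |
| Constant hazard from admission, 10% 28-day risk, exponential lags | 2 v 7 | 0.83 | 1.03 | 1 by construction |
| Identical course from diagnosis | 2 v 7 | 0.70 (1/1.43) | about 1.0 | 0.74 (1/1.35) |
| Identical course from diagnosis | 4 v 7 | 0.78 (1/1.29) | about 1.0 | 0.80 (1/1.25) |

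Under the constant hazard, 28-day risk from diagnosis is 9.2% against 7.7%. That the curves nearly meet by day 28 therefore depends on deaths clustering soon after admission.

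The clock from admission is no worse than the clock as written in any of these scenarios. Delayed entry is unbiased when time since diagnosis drives the hazard or the hazard is constant. It misleads when risk peaks soon after admission.

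**The case against.** **The origin is a legitimate choice and the analysis belongs in the SAP.** Section 8.1 defers analysis detail to separate plans that are not at hand, and the protocol names no survival model for these endpoints. It is true that risk-set handling can sit in the SAP. The origin, however, is fixed in the protocol's endpoint definition, and an SAP that started the clock elsewhere would contradict it.

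**The premises are partly inferred.** Section 5.1 does not make admission an eligibility criterion, and the CCP-UK entry rule is in another document. This stands as a limit, although sections 6.1, 6.4.4 and 8.3.2 all point to admitted patients. A reader might also infer that linked community tests will set the diagnosis date. Section 6.4.3 only lists testing data as a source and does not say so. If diagnosis means the test at admission, the lag is near zero.

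**The size depends on the assumed lags.** This stands. Lags of 2 against 7 days put nearly every patient in one group, and most in the other, as diagnosed before admission.

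**Admission is not a perfect origin either.** This also stands. If time since diagnosis drives the course, the clock from admission leaves a spurious hazard ratio of about 0.74 to 0.80. That is still slightly nearer 1 than the clock as written.

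**Conclusion.** The point holds in a limited form. The stated origin precedes the point at which patients can be observed, so for anyone diagnosed before admission the early follow-up cannot contain a death. The direction is certain for those patients. The size is unknown because the protocol gives no lag distribution. It is negligible if most patients are diagnosed at or after admission, and material for early curves and medians if most are diagnosed earlier (day-14 mortality about 8% against 5% under assumed mean lags of 2 and 7 days). If the course runs from admission and deaths come early, 28-day risk changes little.

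A reader might conclude that the study's fatality rate or its cancer comparisons as a whole are biased by this clock. The documents do not support that. The primary endpoint is binary and analysed by logistic regression (sections 8.3.1 and 8.4.4), so it does not use the clock. The population data in section 6.4.4 are not restricted to hospital cases. The point concerns two secondary endpoints and is worth correcting because the correction is cheap.

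**What to change.** In section 8.3.2:
1. Define the date of COVID-19 diagnosis, including which test or record sets it.
2. Start time to death and time to recovery at the later of COVID-19 diagnosis and hospital admission (CCP-UK entry). This also covers patients diagnosed after admission.
3. Report the diagnosis-to-admission lag by group.
4. Adjust group comparisons for days since diagnosis at entry.
5. Keep delayed entry on the diagnosis clock as a sensitivity analysis only, since it is not interchangeable with item 2.

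The cost is a few sentences and one derived date, with no new data collection. The downside is that the time axis is no longer time since diagnosis, and groups may enter at different stages of disease, which the adjustment addresses only in part.

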## 8.3.3. Exploratory Endpoints

Exploratory endpoints include:

- Baseline microbial diversity measured by microbial diversity index (16s rDNA) in cancer patients compared with non-cancer patients.
- Change in microbial diversity measured by microbial diversity index (16s rDNA) during transition from infection to convalescence in cancer patients compared with non-cancer patients.
- Baseline cancer related microbial species in cancer patients compared with non-cancer patients.
- Change in cancer related microbial species during transition from infection to convalescence in cancer patients compared with non-cancer patients.

### 8.4. Analytical Methods

#### 8.4.1. Patient Groups for Analysis

Primary analysis will be performed on an 'Intention to Treat' (ITT) principles which will analyse all patients identified with cancer and a COVID-19 diagnosis unless there are sound reasons to remove them from the analysis. Various exploratory sub-group analyses may also be performed and these will be fully justified either in the statistical analysis plan or the final statistical report.

#### 8.4.2. Missing Data

Analyses are planned on a complete case basis, however if data on any key covariate are missing at a rate >10% then multiple imputation techniques will be applied.

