# 1 Study Overview

# **1.1.1** Study Overview - CCP-CANCER UK (Companion study)

[figure not shown]
Full Title:	Clinical Characterisation Protocol for Severe Emerging Infections in the UK (CCP-UK) – A prospective companion study for patients with cancer and COVID-19.	
Acronym:	CCP-CANCER UK	
Phase:	Prospective observational cohort study, with routine healthcare data linkage.	
Target Population:	Patients with COVID-19 who have with a diagnosis of a solid or haematological malignancy (D or C codes of ICD-10). The main population will be from patients who have been recruited to the UK Clinical Characterisation Protocol (CCP-UK) study.	
Sample size:	5000 completed datasets	
Inclusion Criteria:	Patients with proven COVID-19 and a diagnosis of cancer, as defined by either a past medical history recorded using the CCP-UK case report form, or who have a recorded diagnosis (C00-D49 ICD-10, or relevant equivalent i.e. ICD-9) in national cancer registries, who are enrolled into any Tier of the Principal CCP-UK protocol.	
Exclusion Criteria:	None in addition to those specified in the Principal CCP-UK protocol.	
Study Centres and Distribution:	Any healthcare facility in the UK who are participating in the CCP-UK study. To ascertain the number of cancer patients in the UK who have had SARS-CoV-2 infection, we will also request linked routine healthcare data for the UK, for all individuals with a cancer diagnosis, not just those in CCP-UK.	
Nature and duration of patient participation:The CCP-CANCER UK companion study involves the coll additional data from patient case records. It does not re additional patient visits, assessments or sample collections as all integral to the Principal CCP-UK protocol.		
Study Duration	There will be three components of the study that run concurrently: Additional data collection for patients in CCP-UK with cancer The study will remain open for at least 2 years post first patient registration onto CCP-CANCER UK. All retrospective patient data collection will begin as soon as each site receives the greenlight to do so,	

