#### 8.2. Sample Size

As the study does not have a pre-defined hypothesis then no formal power calculations are set. Instead, the study is designed to demonstrate defined, precise set of key parameters used to evaluate the study data. It is anticipated, based on accumulating data from the principal CCP-UK study that a conservative estimate of 5000 cancer patients with COVID-19 will be available. With an estimated fatality rate of 10% then a 95% confidence interval will have an approximate length of 3% (e.g. 8.5% - 11.5%).

In terms of evaluating the difference between prognostic factors, conservative estimates of the precision about an odds ratio are considered for a single binary factor with a 70:30 split in prevalence. Here we would expect that a standard error about a log odds ratio of 0.17 to be observed meaning that an odds ratio <0.84 or >1.19 would be determined statistically significant.

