#### 8.4.4. Analysis of the primary endpoint – patient fatality

The primary endpoint is patient fatality measured as the number of deaths as a ratio of the number of patients with a positive COVID-19 diagnosis. Fatality rates will be displayed overall and within different tumour types as a rate with associated 95% confidence intervals.

Further multivariable logistic regression models will be used to evaluate the risk attributable to key demographic/clinical covariates of interest whilst adjusting for possible confounding factors. Results will be presented in terms of an odds ratio and associated 95% confidence intervals.

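### The 10% imputation trigger looks at one covariate at a time and ignores the joint loss of patients from the multivariable risk-factor models

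*Protocol*

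**What the plan says.** Section 8.4.2 sets the rule in one sentence: analyses are "planned on a complete case basis, however if data on any key covariate are missing at a rate >10% then multiple imputation techniques" take over. It does not say which covariates are key, and it sets no limit on the share of patients that a model may lose.

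Section 8.4.4 first reports fatality rates overall and by tumour type. It then says that "multivariable logistic regression models will be used to evaluate the risk attributable to key demographic/clinical covariates of interest", with adjustment for possible confounders. This serves the co-primary objective in Section 3.3 of finding factors associated with poor outcome. The number of covariates per model is not given.

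The Matched Cohort Study part of Section 8.2 states "We will examine the effects of the following variables on mortality and severity of COVID-19 in cancer patients" and lists 14 items:
- age, sex, comorbidities
- tumour type, solid versus haematological disease, bone marrow transplant
- stage at COVID-19, stage at diagnosis, time since diagnosis
- timing of surgery, chemotherapy or radiotherapy; timing of other systemic therapy
- treatment intent, corticosteroids, granulocyte colony-stimulating factor

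Section 8.2 expects that "a conservative estimate of 5000 cancer patients with COVID-19 will be available".

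**The concern.** The trigger and the harm are measured on different scales. The trigger asks how incomplete the worst single covariate is. The harm in a complete-case model is the share of patients with at least one gap. One covariate just over 10% missing, with the rest complete, triggers imputation although only about a tenth of patients would be lost. Fourteen covariates at 5% each never trigger it, although up to half could be lost. The rule can act where little is at stake and stay silent where much is.

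The protocol expects gaps. Section 6.4.3 says that cancer history is absent or wrong for some patients in the parent dataset, and that linked Northern Ireland data are not available at the start. Section 6.4.2 accepts that registry data have varied in quality and quantity over time. The listed variables include "Stage of malignancy at time of COVID-19 (from CCP-UK CRF) and stage at diagnosis from data linkage", so they draw on more than one source.

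At stake are the odds ratios of a co-primary objective. Their intervals widen as patients drop out, and the estimates may be biased if the chance of a gap depends jointly on the outcome and the covariates.

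**Working it through.** **Inputs from the protocol.** N = 5000, fatality 10%, a binary factor split 70:30 (Section 8.2); imputation trigger above 10% for one key covariate (Section 8.4.2); 14 listed variables (Section 8.2).

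**Assumptions, not in the protocol.** A model has k = 8 to 14 covariates that can be incomplete; each is missing at the same rate m between 5% and 10%. 10% is the highest rate that leaves imputation untriggered.

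**1. The plan's own precision figure.** Section 8.4.2 has no figure beyond the 10%. Section 8.2 gives a standard error of 0.17 for a log odds ratio. From the cell counts, SE = sqrt(1/150 + 1/1350 + 1/350 + 1/3150) = 0.103, so 0.17 is not reproduced; it corresponds to about 1831 patients. That is a separate matter. I use 0.103 as the full-data baseline, with 5% significance limits exp(±1.96 × 0.103) = 0.82 and 1.22.

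**2. Joint loss, independent gaps.** Share lost = 1 − (1 − m)^k.
- k = 8, m = 5%: 0.95^8 = 0.663, 34% lost, 3317 left.
- k = 14, m = 5%: 0.95^14 = 0.488, 51% lost, 2438 left.
- k = 14, m = 10%: 0.90^14 = 0.229, 77% lost, 1144 left.

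**3. Joint loss, correlated gaps.** Each gap is driven by a latent normal variable, with equal correlation between covariates. With complete overlap the loss equals m.

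| Setting | m = 5% | m = 7.5% | m = 10% |
|---|---|---|---|
| k = 8, independent | 34% | 46% | 57% |
| k = 11, independent | 43% | 58% | 69% |
| k = 14, independent | 51% | 66% | 77% |
| k = 14, latent correlation 0.6 | 25% | 33% | 40% |
| k = 14, latent correlation 0.8 | 17% | 23% | 29% |
| Complete overlap | 5% | 7.5% | 10% |

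No cell of this table triggers imputation.

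**4. Effect on precision.** SE = 0.1029 / sqrt(share kept), with limits exp(±1.96 × SE).
- 77% lost: 0.1029 / sqrt(0.229) = 0.215; limits 0.66 and 1.52.
- 34% lost: 0.1029 / sqrt(0.663) = 0.126; limits 0.78 and 1.28.
- 40% lost (correlation 0.6, m = 10%): 0.1029 / sqrt(0.597) = 0.133; limits 0.77 and 1.30.
- 10% lost (complete overlap): 0.1029 / sqrt(0.90) = 0.108; limits 0.81 and 1.24.

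These are for one binary factor without adjustment and with the fatality rate unchanged, so they show the relative widening, not the precision of the final models.

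**The case against.** **The large losses need a narrow set of conditions.** Several covariates must each have a material gap, and none may cross 10%. If stage or treatment intent counts as a key covariate and alone passes 10%, imputation applies and the loss disappears. This stands.

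**Fourteen covariates in one model is not in the protocol.** The list gives variables to be examined; Section 8.4.4 speaks of models in the plural. Some items overlap: solid versus haematological follows from tumour type, and stage appears twice. This stands, and is why the range starts at 8.

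**Gaps probably cluster.** There is one cancer report form per patient (Section 6.3) and the linkages are shared (Section 6.4.3). Section 6.4.1 provides for supplying missing data points, Section 6.4.5 for parallel collection from forms and linkage, and Section 6.5 for data queries. This argues for the lower rows of the table. It does not change what the trigger measures. The synopsis target of "5000 completed datasets" does not settle the matter either, since it does not say what makes a dataset complete.

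**Section 8.2 already plans on a standard error of 0.17.** All the correlated cases stay below that figure, as do some of the independent ones. Fair, but the stated 0.17 does not follow from 5000 patients and was not presented as an allowance for missing data.

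**Stronger readings that the text does not support.** A reader might infer a contradiction with Section 8.4.1, where the primary analysis "will analyse all patients identified with cancer and a COVID-19 diagnosis". That sentence goes on to allow removal for sound reasons, and an analysis population is not a missing-data method. A reader might also infer that unstaged or untreated patients would be dropped as missing. Nothing says that not-applicable values are coded as missing, and coding may properly be left to the analysis or data management plan. Finally, a reader might take bias as certain because deaths could have thinner records. No passage says so, and missingness that depends on outcome alone shifts the intercept of a logistic model, not the covariate odds ratios.

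**Conclusion.** The point holds in limited form. The protocol itself fixes the rule, and the rule watches the wrong quantity for multivariable models. The size is conditional: about 34% to 77% of patients lost with 8 to 14 covariates at 5% to 10% missing independently, about 17% to 40% with 14 covariates and latent correlation 0.6 to 0.8, and at most 10% with complete overlap. A reader might infer that half to two thirds of patients will be lost. The documents support that only as a possibility under near-independence with many covariates below the line, because they give neither missingness rates nor model size. The fatality rates overall and by tumour type need no covariate model and are not touched. For the risk-factor models, wider intervals follow directly from the loss; bias is possible, not shown. This is a cheap improvement worth making, not a flaw that undermines the study.

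**What to change.** Amend Section 8.4.2 in one of two ways:
- Trigger multiple imputation on the share of patients who would be excluded from each multivariable model, for example more than 5% to 10%.
- Make multiple imputation the primary approach for the multivariable models from the outset.

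In either case, put the outcome and all model covariates in the imputation model, and report complete case as the sensitivity analysis, with the number of patients excluded from each model.

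The cost is about two sentences and some extra computing. The main downside is that the results then rest on missing-at-random; setting them beside the complete-case results helps a reader judge how much depends on it. Any joint threshold is also a convention, but it is at least applied to the quantity that matters. The second option avoids choosing one.
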